Purpose of clinical study	To determine 
 1. the incidence, the pattern and the recurrence rate of episodes of atrial fibrillation recorded as part of standard clinical care compared to data obtained through extended remote wireless patch-based monitoring for development and validation of health virtual twins and intelligent clinical decision support tools. 2. the occurrence, incidence and character of alerts registered by wCVSM devices and connected applications. 3. the acceptability and usability of post operative continuous real time physiological monitoring according to patients’ and health care professionals’ experiences and views.
Primary objective	To determine the incidence of clinical and subclinical episodes of AF in acutely unwell patients and to generate data for the development and validation of virtual twins and clinical decision support tools.
Secondary objectives	To describe the incidence and character of alerts registered by wireless continuous vital signs monitoring (wCVSM) devices and connected applications (WARD24). To determine patient acceptability and usability for health care professionals of a

	novel remote monitoring device with automated alert function
Number of Subjects	1200 patients of whom 25 participate in both work packages (1 and 2) of the study, and 25 health care professionals who participate in work package 2
Study Design	Single centre mixed methods prospective observational study
Outcomes	
Primary endpoint:
 
 • Occurrence of clinical and subclinical episodes of atrial fibrillation (AF) 
Secondary endpoints:
 
 • ECG characteristics (p-wave duration, amplitude and dispersion, heart rate variability, QTc, incidence of premature atrial complexes) • Serum concentrations of troponin • Echocardiographic markers of atrial function (RWMA score, atrial size and volume, left ventricular strain rate, standard echocardiographic measurements as per BSE recommendations) • Length of stay • Hospital and 90-day Mortality • MAUQ score • Number of AF episodes • Recurrence of AF episodes • Time spent in AF • Time (in hours) wCVSM is attached • Number of cardiovascular alerts • Number of non-cardiovascular alerts • Change in inflammatory markers (white cell count, C-reactive protein and procalcitonin over time)

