Main inclusion and Exclusion Criteria	
Inclusion criteria:
 
 • Adult patients ≥ 50 years • Estimated risk of developing new episodes of AF > 5% • Sinus rhythm at presentation • One of the following acute conditions: 
 ○ Patients admitted or referred to Critical Care (NOTE-AF ICU) ○ Patients admitted to hospital with acute heart failure (NOTE-AF HF) ○ Patients admitted to Emergency Services with sepsis or infection (NOTE-AF Sepsis) ○ Patients post upper gastrointestinal surgery (NOTE-AF PULSE-GI) ○ Patients post vascular interventions (NOTE-AF Vasc) ○ Patients with acute respiratory failure (NOTE-AF Resp) ○ Patients admitted after acute stroke (NOTE-AF stroke) 
Exclusion criteria:
 
 • Atrial fibrillation or atrial flutter at the time of screening • Patients in atrial fibrillation or atrial flutter at time of preoperative assessment or admission to hospital

	
 • Paced cardiac rhythm • Inability to obtain consent • Allergy to plaster or silicone • Expected hospital stay <48h
Randomization	Randomisation is not applicable

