Patients admitted to wards where the WARD247 application is being tested, will be asked to participate. Patients will be asked to complete a questionnaire (Appendix C) to explore their experiences with a remote wireless monitoring system. Health care professionals will participate in semi-structured interviews (Appendix A) and complete the mHealth App Usability Questionnaire (MAUQ) for Standalone mHealth Apps Used by Healthcare Providers a standard questionnaire designed by the University of Pittsburgh (Appendix B). The results and data obtained in this work package will be shared with the WARD24/7 international study team as described in a separate data sharing agreement.

Outcomes for this work package include:

- Number of false alerts
- Number of correct alerts
- MAUQ score
- Semi-quantitative assessment of patient acceptability
- Semi-quantitative assessment of acceptability for nursing and healthcare staff
- Time wCVSM is attached

Study Objectives, Design and Statistics

Research questions and objectives

The **primary research objective** is:

To determine the incidence of clinical and subclinical episodes of AF in acutely unwell patients and to generate data for the development and validation of virtual twins and clinical decision support tools.

The **secondary research objective** is:

To determine patient acceptability and usability for health care professionals of a novel remote monitoring device with automated alert function.

Primary outcome:

The incidence of episodes of AF lasting >30 seconds in acutely unwell and postoperative patients recorded as part of standard clinical care through extended remote wireless patch-based monitoring with or without the use of an alert system (Application).

Secondary outcomes:

Work package 1:

- Length of stay
- Hospital readmissions within 90 days
- Hospital and 90-day Mortality
- Recurrence of AF episodes
- Time spent in AF
- Number of AF episodes
- Complications of AF, e. g. stroke, thromboembolic events
- High sensitivity Troponin concentrations in patients with AF episodes
- Echocardiographic changes in patients with AF episodes

Work package 2:

- MAUQ score
- Percentage change of troponin concentrations in patients with and without episodes of AF
- Time (in hours) wCVSM is attached
- Number of cardiovascular alerts

- Number of non-cardiovascular alerts
- Number of alerts reflecting clinical changes
- Number of alerts reflecting artefacts or non-clinical events

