- RWMA score, atrial size and volume, left ventricular strain rate, standard echocardiographic measurements as per BSE recommendations
- Change in inflammatory markers white cell count, C-reactive protein and procalcitonin over time

Study Design

This is a single centre mixed methods prospective observational study

Statistics

A detailed statistical analysis plan will be developed for the project in line with the objectives for TARGET to achieve the development and validation of dynamic risk prediction tools and virtual health twins.

Sample size considerations:

The primary aim for this study is to generate data for the development of Health Virtual twins as part of the EU Horizon 2023 TARGET project. We will therefore collect a convenience sample of at 1200 patients with a risk of developing episodes of AF of at least 5%. Given evidence from the literature that subclinical episodes that remain undetected may be as high as 30% or more, we expect that in a cohort of 1200 patients at least 60-120 patients will be diagnosed with episodes of AF of at least 30 seconds.

Although the primary aim of the study is to obtain data for the generation of dynamic risk prediction tools and virtual health twins, we will perform a conventional statistical analysis as part of this work:

The primary outcome (incidence of AF episodes >30 sec in acute illness) will be described as ratio of episodes/patient and as percentage of patients having episodes of AF. We will also analyse time spent in AF a percentage of time monitoring was in place, distribution pattern of AF, duration of AF episodes. Occurrence and frequency of premature atrial complexes as precursors of AF episodes.

We will use conventional logistic regression models to establish the correlation and weight between risk factors for AF (e.g. age, cardiovascular comorbidities, organ dysfunction and support, blood pressure, infection status etc.) and occurrence of AF.

Outcomes will be compared in univariate analyses, using parametric or non-parametric test depending on sample distribution.

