Descriptive statistics will be used to describe demographics, frequency of alerts and blood results in patients with and without episodes of AF. Group comparisons will include parametric (T-Test for independent samples) and non-parametric tests (Mann-Whitney-U-Test), depending on sample distributions. For categorical data, Fisher's exact test will be used to examine associations between variables. Monotonic relationships between two numerical variables will be defined using Spearman's rank correlation coefficient.

Where applicable, univariate analysis will be followed by multivariate logistic regression analysis to identify risk factors for the development of AF episodes postoperatively. Cochran–Mantel–Haenszel test (CMH) will be used for the analysis of stratified categorical data, using occurrence of AF >30 seconds as the binary outcome.

Data will be transferred to the data science group at LJMU ([name]) for development and validation of health virtual twins and dynamic risk prediction models in line with the TARGET proposal Work Packages 4 and 5 specific objective (pages 3, SO3 and 34-35, part B of the TARGET proposal): "Development of personalised virtual twin models for dynamic risk prediction of AF and AFRS that consider the patient individual characteristics and medical and health status history. These models are based on novel predisposing factors and will out-perform currently used clinical scores and models." The novel dynamic prediction tools will be compared against conventionally generated logistic regression models.

Sample Size, Selection and Withdrawal of Subjects

Sample size

The primary outcome will be described as ratio of AF episodes/patients. We aim to recruit at least 1200 patients over 40 month with the following characteristics:

- Patients admitted or referred to Critical Care (NOTE-AF ICU)
- Patients admitted to hospital with acute heart failure (NOTE-AF HF)
- Patients admitted to Emergency Services with sepsis or infection (NOTE-AF Sepsis)
- Patients post upper gastrointestinal surgery (NOTE-AF PULSE-GI)
- Patients after surgical vascular interventions (NOTE-AF Vasc)
- Patients with acute respiratory failure (NOTE-AF Resp)
- Patients admitted after acute stroke (NOTE-AF stroke)

We expect to recruit at least 150 patients in each of the above patient groups.

Inclusion criteria for enrolment

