- Data and/or blood samples obtained so far can be used for the research purposes, but no further samples or data will be collected.
- On patient request all data obtained so far will be deleted from the research database in REDCap and all paper documents containing patient data obtained as part of the study will be destroyed. All blood samples obtained will be destroyed.
- The above options will be available on the retrospective consent form.

For patients who were unable to consent for themselves when enrolled in the study, retrospective consent will be sought in written form for them to remain in the study, once they regain capacity (retrospective consent).

Monitoring

Alongside standard care, vital signs will be monitored continuously for seven days after recruitment using the Isansys Lifecare Patient Status Engine (PSE), a CE-marked class 2a medical device, with wireless wearable biosensors recording single-lead continuous ECG, heart rate, heart rate variability, respiratory rate, temperature, oxygen saturation and non-invasive blood pressure, which are displayed on a tablet (Patient Gateway) in real time and securely stored on a server. Alerts can be sent directly to healthcare professionals using authorized mobile devices.

Alternative systems, e. g. Smartcardia platform (SCaAI patch and cloud platform, a CE Class IIa approved system with monitoring of 7-lead ECG, respiration, SpO₂, activity and cloud-based arrhythmia detection, may be used.

Blood sampling

Surplus serum blood samples will be collected on the day of recruitment (day 1), until day7 and within 24h before hospital discharge. Where a blood sample has been requested for clinical reasons, a serum blood sample will be added to the request if not yet included. Pseudonymized samples will be centrifuged, plasma or serum will be aliquoted, frozen and stored at -80°C for subsequent analysis. Serum samples will be transferred to the Liverpool Biobank at regular intervals to be available for future research. Serum samples will be used to determine cardiac biomarkers, including but not limited to troponins and natriuretic peptides and inflammatory markers, including but not limited to cytokines and interleukins. Samples of patients who decline use in future research will remain stored at freezers within the Liverpool University Hospitals NHS Foundation Trust and destroyed after this project has finished. A detailed flow diagram of blood sampling is provided in Appendix I.

Biomarker testing

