Appendix E. Study procedures

	Screening / Pre-study	1	2	3	Day 3-7	Discharge	Day 90
Inclusion and Exclusion criteria	X						
Medical history (preexisting condition, premedication)	X						
Consent	X						
Demographic data	X						
Admission diagnosis, Category of admission (elective, emergency)		X					
Surgical parameters (type & duration of procedure, intraoperative transfusion)		X					
APACHE II		X					
SOFA Score		X	X	X			
Standard vital signs (SBP, DBP, MAP, HR, RR, SpO2, if indicated CVP, CO)	X	X	X	X			
Continuous Vital Signs monitoring		X	X	X	X		
Laboratory parameters (if clinically indicated)		X	X	X	X	X	
Collection of surplus routine blood samples (when available)	X	X	X	X	X	X	
Transthoracic Echocardiography (if clinically indicated and available)	X	X	X	X			
Vasopressor and inotrope use	X	X	X	X	X		
Documented episodes of AF (in clinical notes and on wCVSM)		X	X	X	X	X	X
Concomitant cardiac Medication (antiarrhythmics, diuretics, statins, antihypertensives)	X	X	X	X	X	X	X
Mortality						X	X
EQ-5D-5L						x	x
Duration of organ support (Begin and end of RRT, mechanical ventilation, oxygen therapy)	X	X	X	X	X	X	X
Length of stay (ICU, Hospital)					X	X	X
Cardiac Recovery							X
Cardiac diagnoses / complications (episodes of AF; congestive heart failure, thromboembolic event, stroke)	X	X	X	X	X	X	X
Non-cardiac diagnoses / complications (sepsis, pneumonia, wound infection, anastomotic leak, bleeds)		X	X	X	X	X	X

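### The primary outcome merges standard-care and patch-detected AF, so the plan does not deliver the clinical/subclinical split it names, and no rule attributes AF first noticed on the live device

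*Protocol*

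**What the plan says.** The first purpose in the Study Synopsis is a contrast between two sources of detection: AF "recorded as part of standard clinical care compared to data obtained through extended remote wireless patch-based monitoring". The primary objective is consistent with that: "To determine the incidence of clinical and subclinical episodes of AF in acutely unwell patients".

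The primary outcome under Research questions and objectives is worded differently: episodes longer than 30 seconds "recorded as part of standard clinical care through extended remote wireless patch-based monitoring with or without the use of an alert system". The Statistics section says that this outcome "will be described as ratio of episodes/patient and as percentage of patients having episodes of AF". It does not divide either summary by source of detection.

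Both sources exist in every patient. There is no allocation ("Randomisation is not applicable" in the synopsis), the patch runs for seven days on top of usual care, and the schedule in Appendix E has a row for "Documented episodes of AF (in clinical notes and on wCVSM".

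The Monitoring section says that patch signals appear on a bedside tablet in real time, and "Alerts can be sent directly to healthcare professionals using authorized mobile devices". The protocol describes neither masking of ward staff to the display nor a rule for deciding when an episode counts as detected by standard care.

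**The concern.** Two things are at stake, and both concern AF that usual care does not see, which the synopsis gives as the rationale for continuous monitoring.

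First, without the words that make it a comparison, the primary outcome can be read as AF on the patch, AF in the notes, or AF in either. These are different quantities. None of them, reported alone, shows how much AF was clinical and how much subclinical. An analysis plan could settle this only by choosing between conflicting protocol statements.

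Second, the standard-care side is observed while the study device is visible to the people delivering that care. AF that a nurse first sees on the tablet or in an alert can enter the notes and be counted as clinically detected. That moves patients out of the missed group and makes usual care look better at finding AF than it would be without the device. What prompted recognition may not be recoverable from the notes later, so this is a matter of data capture as well as analysis.

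**Working it through.** **1. The two statements side by side.** The synopsis purpose has standard care, then *compared to data obtained through*, then patch monitoring. The primary outcome has standard care, then *through*, then patch monitoring. The comparison is gone and the patch has become part of standard care. The phrase about use with or without alerts also pools two conditions under which staff have different access to the patch data.

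**2. The protocol's own figure.** Statistics expects at least 60 to 120 AF patients among 1200. The lower end reproduces: 1200 × 0.05 = 60. The upper end needs a 10% risk (1200 × 0.10 = 120), which that sentence does not state. The point does not depend on this figure; both ends are used below for scale.

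**3. What the ambiguity does to the incidence.** Assumptions: the patch finds every case, and standard care misses 30% of AF patients. The protocol gives 30% or more for undetected subclinical episodes; applying it to patients is an assumption.

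| AF patients | Missed by standard care | Found by standard care | Incidence, patch or either source | Incidence, notes only |
|---|---|---|---|---|
| 60 | 60 × 0.30 = 18 | 42 | 60/1200 = 5.0% | 42/1200 = 3.5% |
| 120 | 120 × 0.30 = 36 | 84 | 120/1200 = 10.0% | 84/1200 = 7.0% |

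The same sentence supports 5.0% or 3.5%, or 10.0% or 7.0%. A pooled 5.0% on its own is compatible with any missed share from none to all.

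**4. What device-prompted recognition does to the missed share.** Let m be the share truly missed without the device and q the fraction of those that staff pick up because of the display or an alert. Then

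apparent missed share = m × (1 − q).

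With m = 0.30:
- q = 0.25: 0.30 × 0.75 = 22.5%
- q = 0.50: 0.30 × 0.50 = 15%
- q = 0.75: 0.30 × 0.25 = 7.5%

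The values of q are assumed. The protocol gives none, and does not say how many patients have alerts active.

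**5. Against sampling error.** The simple 95% half-width for a share of 30% is 1.96 × √(0.30 × 0.70 / n). For n = 60 it is 1.96 × 0.0592 = 11.6 points; for n = 120 it is 1.96 × 0.0418 = 8.2 points. A shift of 7.5 points (q = 0.25) lies inside either half-width. A shift of 15 points (q = 0.50) lies outside both.

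**6. Why the missed share should be given both ways.** Take 60 patch-AF patients, 18 truly missed, q = 0.50, so 9 come to light through the device. Suppose also that 6 of the other 42 were first noticed on the device although routine care would have found them later (assumed). Counting device-prompted cases as found gives 9/60 = 15%. Counting them all as missed gives (9 + 9 + 6)/60 = 40%. The true 30% lies between, and neither count alone recovers it.

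**7. Same hours.** The patch runs for seven days, but the AF row in Appendix E continues to discharge and day 90. Unless both sources are restricted to the monitored hours, AF in the notes after the patch is removed would be set against a period the patch could not see.

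**The case against.** Several counter-arguments carry weight.

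- *The contrast is not wholly lost.* Clinical and subclinical AF remain in the primary endpoint and objective, and Appendix E collects both sources. This is right: the data for the contrast will exist. What is missing is an outcome statement and summary that use them, and the conflict between synopsis and body remains.
- *Incidence is safe.* The background sections on postoperative AF and on wireless monitoring say the patch will identify AF over 30 seconds whether or not clinicians recognise it. This also stands. Device-prompted recognition affects the clinical/subclinical split and the standard-care rate, and leaves total patch-detected incidence largely unchanged. A reader who inferred that the headline patch incidence is biased would go beyond the documents.
- *Exposure may be small.* The WARD application belongs to work package 2, with 25 of 1200 patients (about 2%), and the Monitoring section says only that alerts can be sent. However, that section does not limit device alerts to those patients, and the tablet display is described for all. Exposure is therefore unknown.
- *Test choice.* A reader might infer that the protocol analyses this paired contrast with an unpaired test, since Fisher's "exact test will be used to examine associations between variables" and no paired test is named. The documents do not support this. That paragraph concerns patients who had AF against those who did not, who are independent groups. Nothing assigns Fisher's test or the Cochran–Mantel–Haenszel test to patch versus standard care. The synopsis also names mixed-effects models and refers to an analysis plan, where the choice of test can properly be made.

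**Conclusion.** The point holds in two parts. The synopsis purpose and the primary outcome contradict each other, and the pooled summary does not yield the split named in the primary objective. This rests on the text alone. Separately, live display and possible alerts, with no attribution rule, can make the missed share look smaller than it is. That is a design risk of unknown size: from 30%, the apparent share would be 22.5%, 15% or 7.5% at assumed pick-up rates of 25%, 50% and 75%. The illustration assumes that the patch finds every case and that the protocol's 30% applies to patients. Nothing here shows that the protocol uses a wrong test or a wrong variance, and total patch-detected incidence is not in question on this ground.

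**What to change.** 1. Reconcile the synopsis and the body. State the primary outcome as patients with at least one AF episode longer than 30 seconds, detected (a) by the patch and (b) in standard care, over the same monitored hours. Define clinical and subclinical AF in those terms.
2. Report the share of patch-AF patients not found by standard care, with a 95% CI, and treat the two detections as paired within patient. The specific method can be left to the analysis plan.
3. Add one eCRF field for what prompted first recognition: wCVSM display or alert, other, unknown. Record whether alerts were active and report results by that status.
4. Give the missed share twice, with device-prompted recognitions counted as missed and then as found, and present the two as bounds. Counting all of them as missed overstates the share when routine care would have found some later. Handle unknown prompts the same way.

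The cost is a wording change and one field, with no change to monitoring or to what staff see. The downside is that some prompts will go unrecorded, which widens the bounds. The field should be in place before recruitment, or as early in it as possible.

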- Adult patients ≥ 50 years undergoing major upper gastrointestinal or vascular surgery or admitted to hospital with at least one of the following acute conditions associated with an estimated risk of developing episodes of AF $>5\%$:
 - Acute respiratory failure
 - Any acute illness referred or admitted for higher level of care (level 2 or 3)
 - Patients with acute stroke
 - Patients with acute heart failure
 - Patients admitted to the emergency department with clinical suspicion of severe acute infection or sepsis requiring hospitalisation
- Sinus rhythm at preoperative assessment

Exclusion criteria for enrolment

- Atrial fibrillation or atrial flutter at the time of screening
- Patients in atrial fibrillation or atrial flutter at time of preoperative assessment or admission to hospital
- Paced cardiac rhythm
- Inability to obtain consent (patient and/or consultees decline study participation)
- Allergy to plaster or silicone
- Expected hospital stay <48 h

Criteria for Premature Withdrawal

- Withdrawal of consent
- Intolerance of monitoring patch
- Persisting skin irritation at patch site

Study procedures

Screening Procedures

Patients with acute conditions listed above or who are scheduled to have vascular or major upper GI surgery will be screened against the inclusion and exclusion criteria.

Consent and Enrolment Procedures

We wish to include a wide range of patients admitted to various to acute care wards, e. g. emergency departments, acute medical wards, surgical wards and higher level of care units (level 2 and level 3) within the hospital. Thus, we expect patients with a wide range of cognitive function, reaching from normal mental capacity to confusion to severely impaired cognitive function to be included: While patients with planned surgery, e. g. major elective abdominal or vascular surgery, will be able to consent for themselves before the operation, patients undergoing emergency surgery, may have altered cognitive function, which will impair their capacity to consent for themselves. Similarly, patients with severe acute medical disease, e. g. sepsis may be acutely confused and therefore not able to consent for themselves. We will assess capacity for each patient before approaching them for consent, adhering to the principles outlined in the British Medical Association Ethics Toolkit

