- The Professional Consultee may request that the patient is withdrawn at any stage as outlined above (as explicitly stated in the 'Professional Consultee Information Sheet').
- When the patient regains capacity, the research team will speak to the patient at the earliest opportunity and invite the patient to give consent to continue participation; if the patient chooses to continue to participate in the study they will sign a 'Consent Form (Continuation)'; if the patient gives consent, they are free to withdraw their consent at a later stage as outlined above; if the patient does not wish to consent, they will be withdrawn from the study.
- If the patient never regains capacity or dies, he/she will remain in the study. In this case we plan to include their outcome data until day of death and biological samples in the final analysis.

If patients do not have capacity to consent and a personal consultee is not immediately available, we will consult with a professional consultee (as outlined above) according to the emergency provision of the Mental Capacity Act. If the patient has capacity or a personal consultee is available, it is hoped that they will not need longer than 3 hours to make a decision regarding participation in the study. However, if patients or their personal consultees need longer to make an informed decision, this will be acknowledged. If participation is still possible within the limited time period, this will be facilitated. Otherwise, the patient will not be included.

Having consented, a patient can change their mind and withdraw from the study at any time between consent and completion of the study. Patients can withdraw consent at any time during the intervention period and later. If they withdraw during the intervention period, they will be asked if the withdrawal should apply to study data collected, and/or samples collected and/or sample analysis and if data and samples obtained so far can be used for study purposes.

A patient who decides to withdraw from the study can do so for any reason, without prejudice and without an impact on their clinical care.

A patient who was enrolled into the study following consultation with a personal or professional consultee may also be withdrawn from the study at the request of his/her legal representative or the professional consultee, for any reason and without prejudice. For patients who withdraw consent, the following options will be offered

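### AF incidence is the primary outcome, but patients are a convenience sample with no rule on which eligible patients are approached and no record of those not enrolled

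*Protocol*

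**What the plan says.** The primary objective, given in the synopsis, in the description of work package 1 and under Research questions and objectives, has two parts. It begins "To determine the incidence of clinical and subclinical episodes of AF in acutely unwell patients and to generate data", the data being for virtual twins and decision support tools. The primary outcome is the incidence of AF episodes longer than 30 seconds. Under Statistics it "will be described as ratio of episodes/patient and as percentage of patients having episodes of AF".

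Under Sample size considerations the order of priority is different: "The primary aim for this study is to generate data for the development of Health Virtual twins". The next sentence draws the sampling method from that aim: "We will therefore collect a convenience sample of at 1200 patients with a risk of developing episodes of AF of at least 5" per cent. The same paragraph expects that "at least 60-120 patients will be diagnosed with episodes of AF of at least 30 seconds".

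The later section on sample size and selection lists seven patient groups, with at least 150 patients expected in each. Under Screening Procedures, patients with the listed conditions or planned operations "will be screened against the inclusion and exclusion criteria". Consent and Enrolment Procedures sets the timing (before surgery, or as soon as possible after admission) and three consent routes: the patient, a personal consultee or a professional consultee.

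**The concern.** A convenience sample can serve a study whose purpose is to collect data for model building. It is a weak basis for the other half of this primary objective, a statement about how often AF occurs in acutely unwell patients. That percentage carries over to eligible patients only if those enrolled resemble those who were eligible. The protocol gives a reason for convenience sampling that concerns the modelling aim alone, and none for incidence.

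The synopsis rationale presents the unknown true incidence of AF in acutely unwell patients as a gap to be filled. If enrolment within a cohort depends on anything related to AF risk, the figure will be wrong by an amount that the confidence interval does not show. With no log of eligible patients who were not enrolled, nobody can later judge whether this happened. The modelling aim is not wholly protected either, because the calibration of an absolute-risk model depends on how frequent the outcome is in the development cohort.

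**Working it through.** **1. The plan's own figure.** 1200 × 5% = 60, and 1200 × 10% = 120. The expected 60 to 120 patients with AF is consistent with rates of 5% (stated) and 10% (implied). The 1200 itself comes from no power or precision formula.

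**2. Sampling error.** Half-width = 1.96 × √(p(1−p)/n).

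| p | n = 1200 (whole study) | n = 150 (one group at its expected minimum) |
|---|---|---|
| 5% | 1.2 points | 3.5 points |
| 10% | 1.7 points | 4.8 points |

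These figures describe chance variation only. They assume that the enrolled patients represent the eligible ones.

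**3. What governs who is enrolled.** Taking the sections in turn:

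- *Inclusion and exclusion criteria:* who qualifies. This is defined.
- *Sample size:* an expected minimum per group, 7 × 150 = 1050. The remaining 1200 − 1050 = 150 places have no stated allocation.
- *Screening Procedures:* qualifying patients are checked against the criteria. Nothing says all, consecutive or randomly chosen, and no log is required.
- *Consent and Enrolment Procedures:* when to approach and by which consent route. Nothing says which eligible patients, or in what order.

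No section supplies the missing rule.

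**4. Why the size and direction stay open.** Let r be the chance that an eligible patient who will have AF is enrolled, relative to one who will not. The observed proportion is then p·r / (p·r + 1 − p). The documents give no value for r, so the values below are assumptions on both sides of 1.

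| True p | r = 0.5 | r = 0.8 | r = 1.25 | r = 2 |
|---|---|---|---|---|
| 5% | 2.6% | 4.0% | 6.2% | 9.5% |
| 10% | 5.3% | 8.2% | 12.2% | 18.2% |

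For example, with p = 10% and r = 0.5: 0.05 / 0.95 = 5.3%. At r = 0.8 or 1.25 the shift is about the size of the whole-study half-width, and at 0.5 or 2 it is larger. This is not an estimate for this study. It shows only that a narrow interval does not limit selection error and that the error can go either way.

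**5. Cohort mix.** The pooled percentage also depends on where the 150 unallocated places go. Assume six groups at 5% and one at 45.5%, the highest figure the protocol cites (for oesophageal resection). With the places outside the high-rate group: (1050 × 0.05 + 150 × 0.455) / 1200 = 10.1%. With all of them inside it: (900 × 0.05 + 300 × 0.455) / 1200 = 15.1%. If all groups had the same rate, the shift would be zero. This is a reason to report by cohort.

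**The case against.** The strongest reply is that the protocol discloses the convenience sample, names data generation as the primary aim and treats the conventional analysis as an accompaniment. On that view, convenience sampling in a single-centre observational study is a limitation to report. The modelling aim does come first in the sample size section, and that stands. But the same protocol states incidence as part of the primary objective in three places and makes it the primary outcome, so the mismatch remains.

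A second reply is that the protocol works to avoid the obvious selection. It expects patients with severely impaired cognition, applies its tiered consent approach in every care setting, makes Critical Care a cohort of its own and calls the inclusion of emergency patients necessary because of their AF risk. This is right, and it weakens any claim that only alert, stable patients will be enrolled. Consent routes do not, however, settle which eligible patients are approached.

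Third, the analysis may be left to a statistical analysis plan. That holds for weighting methods. It does not hold for the order of approach or a screening log, which are matters of conduct: data not recorded during recruitment cannot be supplied by an analysis plan.

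A reader might also infer more than the text allows:

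- *That incidence will be too low because high-risk emergency patients are harder to enrol.* Elective surgical patients are the ones expected to consent for themselves in advance, and oesophageal resection carries the highest rate cited. Over-enrolling them would raise the pooled figure.
- *That the consent time limit excludes patients without capacity.* The sentence "Otherwise, the patient will not be included" follows a provision that covers patients with capacity as well as personal consultees. Where no personal consultee is immediately available, a professional consultee is used.
- *That the study has no defined population.* Age, rhythm, conditions and exclusions are all stated. What is missing is how patients are taken from that population.

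**Conclusion.** The point holds as a mismatch between sampling method and objective. Incidence is a primary result, the sample is one of convenience, and no rule or record links those enrolled to those eligible. The percentage may be distorted by selection. Distortion is a risk here and not an established fact, and the documents support no figure for its size and no statement of its direction. The conclusion rests on the protocol text alone, and it assumes that no separate recruitment procedure, not shown, already requires consecutive approach and a screening log. The change is worth making and cheap. It does not call the modelling aim or the choice of 1200 patients into question.

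**What to change.** 1. Under Sample size considerations, replace the convenience sample with consecutive approach of eligible patients within pre-set recruitment sessions for each cohort. Record the days and hours of the sessions, since sessions confined to certain hours would still select by time of day.
2. Keep a non-identifying log from the screening step already planned: cohort, age band, sex, emergency or elective, and reason not enrolled. Record capacity only where it was assessed, because the protocol assesses it before the consent approach and patients never approached may have no assessment.
3. Report incidence by cohort alongside the numbers screened and enrolled. As a sensitivity analysis, add a simple standardisation to the screened eligible patients. Keep it simple: 60 to 120 expected cases over seven cohorts average about 9 to 17 per cohort (60/7 and 120/7), too few for stable weighting on several factors. It can correct only for characteristics that were logged.
4. If consecutive approach is not achieved, limit the incidence conclusion to the enrolled cohort.

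The cost is a change of protocol wording, a short log, one extra analysis and slightly less flexible recruitment. The log has to run during recruitment, so it cannot be left to the analysis stage.
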